### **3. Study Design**

The study is a Phase 1 dosing and tolerability study of TIL-TC150. TIL-TC150 will be administered to 20 children with Dravet syndrome by the investigator team who will closely follow them for the duration of the study.

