#### **3.1 Pre-intervention period (4 weeks)**

This period is the first four weeks after the patient is enrolled. Once enrolled, the participant's legal guardian will be educated about maintaining a detailed seizure diary during this 4 week period to allow baseline analysis of seizure frequency. As an objective measure of seizure frequency, during this 4 week period all enrolled

participants will undergo a 24 hour ambulatory EEG study to also assess ictal and interictal epileptiform activity.

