#### **4. Selection and Withdrawal of Participants**

##### **4.1 Inclusion Criteria**

Participants selected for the study must meet the following criteria:

1. Age between 12 months and 18 years
2. Parent/ legal guardian informed consent obtained
3. Clinical and EEG (sleep recording within 12 months of study enrollment) characteristics of Dravet Syndrome and confirmatory genetic mutation result
4. Medication-resistant epilepsy – with failure to achieve seizure control with at least 2 appropriate AEDs at therapeutic doses
5. Clinically apparent seizures (excluding myoclonic and absence) occurring at least twice per week
6. Agreed diary compliance and clinical compliance with current prescribed therapy
7. Concomitant AED medication dosing stable during 4 week pre-intervention period. Ketogenic diet regime and VNS device settings must be stable for 3 months prior to pre-intervention period.
8. Ability to tolerate administration of medication orally or via percutaneous feeding tube (PEG).
9. Negative urinary pregnancy test for all female participants of child bearing age

10. Was never on Cannabinoid therapy or have not been treated with Cannabinoid products for at least last 60 days (confirmed by negative urine test for Tetrahydrocannabinol (THC), only for those who had been treated with CBD).

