#### 4.3 Recruitment

20 participants will be recruited by the study investigators from their epilepsy clinics at The Hospital for Sick Children. During a routine visit, patients/parents/caregivers that meet criteria for the study will be asked if they would like to participate in the study. If they are interested in participation then eligibility will be assessed using our inclusion

and exclusion criteria. Patients who have previously been treated with a Cannabinoid product, must have stopped taking it at least 60 days before enrolment, and they will be asked for a urine test (5-10 ml) to assess for the presence of Tetrahydrocannabinol (THC) in urine. A negative urine test for THC will confirm their eligibility to the study. There is published clinical trial evidence for Epidiolex (a cannabinoid product) as an anti-epileptic agent, and Health Canada approved Cannabinoid product use over a year ago, therefore many families have tried this product, and it is not feasible to expect CBD naïve participants, nor is it necessary. A washout period is sufficient. A wash out period of 60 days allows for all of the administered cannabinoid products to be eliminated from the participant's body. All genders and ethnicities will be included between ages of one and eighteen years. The physician will explain the study during the routine visit. If the patient/parent/caregiver agrees, they will be given the informed consent documents to read and sign. Only the Principal Investigator, Sub-Investigators, and other research personnel listed on the study will have access to participant's research files.

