#### 4.4.3 Replacement

Participants will not be replaced following withdrawal in the study

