### 5.5 Pre-Intervention Period (4 weeks)

Once enrolled, the pre-intervention period begins. Participants will be seen and baseline physical and neurological examination performed. Medical information regarding seizures, medications, birth and development will also be collected. Participant parent / legal guardian will be instructed to keep a daily seizure diary for the next four weeks which will be used as a measure of baseline seizure frequency. Seizure diary will be kept by participant's parent/ legal guardian for the duration of the study follow-up period also. Seizure frequency for each seizure type will be recorded at baseline. Seizure types will be classified prior to study entry.

- A. Diary: Seizure frequency and type will be monitored and recorded in a participant's daily diary. Participant's parent/caregiver will report the seizure frequency, type, number of episodes of Status Epilepticus, use of rescue medication and attendance to ER/ hospitalizations.
- B. Prolonged EEG study: During the pre-intervention period each participant will have a 24 hour ambulatory EEG recording performed to enable objective measurement of a 24 hour sample of electrographic activity – ictal and interictal, which will be reported by a certified experienced Clinical Neurophysiologist who is not part of the investigator team.
- C. Vineland Adaptive Behaviour Scale, Second Edition: this is a standardized parent interview that will take 20-60 minutes to complete either in person at the clinic or by telephone prior to starting the TIL-TC150. The interview will also be completed again at the primary evaluation period (week 16-20) and again during the longitudinal follow-up (52-64 weeks). This will be done by a clinical research assistant, under supervision of a clinical neuropsychologist (Dr. [name], CPsych). Parents will be provided with a research report detailing the assessment findings at study completion.

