## **8. Statistics**

### **8.1 Statistical Method**

This is an observational study. The primary aims of this study are to determine the tolerability of the study treatment in a cohort of children with medication resistant epilepsy due to Dravet syndrome. As such, there are no formal statistical methods required, rather descriptive statistics will be presented to quantify dosing tolerability and frequency of adverse events. All participants will be analyzed regardless of dose achieved or duration of study completed, according to intention to treat analysis. The study data will be entered into the REDCap database for analysis.

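### Section 8.1 defines no treated population, so a child enrolled at Week -4 but lost before the first dose would, read literally, stay in the adverse-event and tolerability denominator

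*Combined protocol and SAP*

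**What the plan says.** The analysis rule is one sentence in section 8.1: "All participants will be analyzed regardless of dose achieved or duration of study completed, according to intention to treat analysis". The outputs are described just before it: "descriptive statistics will be presented to quantify dosing tolerability and frequency of adverse events". No safety, treated or other analysis set is defined anywhere in the document.

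Participation starts before treatment. Section 3.1 says of the pre-intervention period: "This period is the first four weeks after the patient is enrolled". Section 5.5 agrees: "Once enrolled, the pre-intervention period begins". The schedule in 5.8 puts this at Week -4, and section 5.2 puts the first dose at Week 0.

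One entry criterion runs through that interval. Inclusion criterion 7 in section 4.1 requires: "Concomitant AED medication dosing stable during 4 week pre-intervention period". Section 4.4.1 allows withdrawal at any point, and section 4.4.3 adds: "Participants will not be replaced following withdrawal in the study". Section 7.1 opens the adverse-event reporting period when study treatment starts.

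On numbers, section 4.3 says "20 participants will be recruited by the study investigators", and section 8.2 likewise describes 20 as the number expected to be recruited. Section 3 says "TIL-TC150 will be administered to 20 children with Dravet syndrome".

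**The concern.** Intention to treat preserves the comparison that randomisation creates. This study has one arm and no randomisation, so counting children from enrolment protects nothing. It can only bring in children with no exposure to the product.

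Such a child cannot have a reportable adverse event, because reporting opens at the first dose, yet would still count in the denominator. Adverse-event frequency would then err in the reassuring direction, in the analysis that carries the primary aim.

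For tolerability and dose reached, an undosed child carries no information. Depending on how the child is coded, a summary could look better or worse. The plan gives no coding rule, so the choice would be made in an open-label study after the data are known.

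**Working it through.** The plan has no calculation to reproduce. Section 8.2 says that no sample size calculation was made, and no dropout allowance is given.

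**Can a child be a participant without being dosed?**

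1. Enrolment is at Week -4 (3.1, 5.5, 5.8) and the first dose at Week 0 (5.2).
2. AED stability over those four weeks (criterion 7) cannot be confirmed until they end.
3. Withdrawal is open throughout (4.4.1), and one listed ground is failure to follow study procedures. The diary and the 24-hour EEG are procedures of this period.
4. No rule covers a child lost in this interval. Section 8.1 makes no exception.

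So the wording leaves such a child in the analysis.

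**How much would it matter?**

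Inputs: 20 enrolled (4.3, 8.2); illustrative true rates of 25% for somnolence and 19% for diarrhea, the rates section 1.7.1 cites from an earlier open-label study; k children enrolled but never dosed, which is an assumption.

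Reported proportion = true proportion x (20-k)/20, since undosed children have no events by definition. Example, k = 2: 25% x 18/20 = 22.5%.

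One-sided 95% upper bound when no event is seen = 1 - 0.05^(1/n). With n = 20 this is 13.9%; with n = 18 it is 15.3%. The plan does not ask for this bound; it shows what zero events out of the stated number would imply.

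| k | dosed | factor | true 25% shown as | true 19% shown as | bound if 20 counted | bound on dosed |
|---|---|---|---|---|---|---|
| 0 | 20 | 1.00 | 25.0% | 19.0% | 13.9% | 13.9% |
| 1 | 19 | 0.95 | 23.8% | 18.1% | 13.9% | 14.6% |
| 2 | 18 | 0.90 | 22.5% | 17.1% | 13.9% | 15.3% |
| 4 | 16 | 0.80 | 20.0% | 15.2% | 13.9% | 17.1% |

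For scale against sampling error, suppose five children have an event (exact 95% intervals):

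- Counting 20: 5/20 = 25.0% (8.7 to 49.1).
- Counting 18 dosed: 5/18 = 27.8% (9.7 to 53.5).
- Counting 16 dosed: 5/16 = 31.3% (11.0 to 58.7).

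The shift is systematic but small beside the imprecision.

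**The case against.** The strongest reply is that the plan already has treated children in mind. Section 5.2 has each participant start on the initial dose. Section 3 describes 20 children receiving the product. The study summary reports adverse events by the dosages used, and an undosed child belongs to none of these. The reference in 8.1 to dose achieved most naturally means the titration level reached. The text on withdrawal in 4.4 largely presupposes treatment, and section 5.4 invites children who already meet the criteria. Much of this stands as evidence of intent, and it limits the dilution to proportions taken over all participants. But these passages describe conduct and do not define an analysis set; the one sentence that does names all participants. Section 5.4 also cannot settle a criterion that is measured after enrolment.

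Some stronger readings are tempting, and the documents do not support them:

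- A reader might infer that undosed children will certainly enter the denominators. That happens only if a child is lost before Week 0, and no such number is given.
- A reader might infer that these children enter the dose summary as zeros. No coding rule says so.
- A reader might count diary failure before Week 0 as failed eligibility. Inclusion criterion 6 is an undertaking given at entry, so a later lapse is non-compliance under 4.4.1.
- A reader might put the distortion at 7 to 15 percentage points, for example 12/20 = 60% against 12/18 = 67% or 12/16 = 75%. That needs an assumed 60% event rate. At the cited 25%, the shift for k = 2 to 4 is 2.5 to 5 points.
- A reader might infer that the no-replacement rule must change or that re-screening is needed. Section 8.2 calls 20 a convenience sample, so dosing 18 or 19 breaches no stated target. Those are design preferences.

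**Conclusion.** The gap is real, and closing it is a cheap improvement. As worded, section 8.1 would keep a child lost between Week -4 and the first dose in the adverse-event and tolerability denominator. The resulting understatement of adverse-event rates is 5% in relative terms for each undosed child, given 20 enrolled.

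The conclusion rests on a literal reading of 8.1 and on at least one pre-dose loss. The size is known only for assumed values of k. For tolerability, even the direction cannot be stated, because the coding of an undosed child is not given. No test, power or precision target depends on the choice, so the harm is confined to descriptive rates that could look somewhat too favourable.

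The figure of 20 is also ambiguous: sections 4.3 and 8.2 speak of recruitment and section 3 of children dosed. With no replacement, the two agree only if nobody is lost before Week 0.

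**What to change.** In section 8.1, replace the intention-to-treat wording for safety, tolerability and dose summaries with a treated population: every child who receives at least one dose of TIL-TC150, whatever dose level is reached and however long the child stays in the study. This keeps the useful part of the present rule, that nobody is dropped for stopping early or titrating less far.

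Report children enrolled but never dosed separately in the participant flow, with reasons. State in sections 3, 4.3 and 8.2 whether 20 means enrolled or dosed.

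The cost is a few sentences. The small downside is that the denominator may fall below 20 and the reported adverse-event rates become slightly less favourable. No visit, dose or withdrawal rule changes.

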### **8.2 Sample Size**

No sample size calculation was employed. An intermediate sample size of convenience is selected, with 20 participants expected to be recruited from a single site.

## **9. Source Data/Documents Access**

The study investigator team will permit trial-related monitoring, audits, REB review, and regulatory inspections, providing direct access to source data/documents.

## **10. Quality Control Procedures**

The study pharmacist will oversee the dispensing of the study treatment to the participant parent/caregiver and keep documentation of this. Study investigators will document all clinical details throughout the study in CRFs and in source documentation. Principal investigator will make time to review the documentation, source documentation and ensure that it is readily available for any reviewing agency at any time. In addition study investigator team will ensure confidentiality is maintained throughout the data process. This will be overseen by study Principal Investigator as detailed below.

## **11. Study Ethics**

This study is conducted in accordance with applicable Health Canada regulations and international standards of Good Clinical Practice, and applicable institutional policies and procedures.

## **12. Data Handling and Record Keeping**

### 12.1 Confidentiality

Study participant medical information will be recorded for this study. Any participant identifier information and personal health information will be stored in a locked filing cabinet in a locked office at The Hospital for Sick Children and only the investigational team will have access to this.

### 12.2 Data Storage

Relevant study records will be archived for 25 years following completion of the study, as per the requirements of Health Canada's Food & Drug Act, Division 5.

## **13. Trial Registration**

This trial will be registered with the U.S. National Institutes of Health ClinicalTrials.gov, which is a registry of federally and privately supported clinical trials conducted in the

United States and around the world. The registration will not include any identifiable participant data.

#### **14. Publication policy**

On completion of the study the enrolled participant data will be reported and this report submitted for publication in an appropriate medical journal.

